9.3.2.7 Imputation Rule

In this study, the imputation methods are only intended for the diary data collected in the e-diary and secondary variables (i.e., MSQ v2.1 RFR domain score, AIM-D Physical Impairment domain score, HIT-6 score). No imputation will occur for other variables.

If a subject reports any diary data for less than 14 days of a 28-day period, the subject's scores (such as headache day count) for that period will be set to missing for summary tables of observed data. For tables of imputed data, such a subject's score for that period will be imputed by a modified last observation carried forward (mLOCF) rate-change method and rounded to the nearest whole number. Specifically, the substitution will be the subject's previous 28-day period score multiplied by the ratio of the mean within the same treatment regimen in the 28-day period of interest to the mean within the same treatment regimen in the previous 28-day period.

If a subject reports diary data for at least 14 days of a 28-day period, the scores for the period will be determined by the simple prorating method (discussed in Section [9.3.2.5](#)).

If a subject reports any diary data for less than 4 days of a 7-day period, the subject's scores (such as headache day count) for that period will be set to missing for summary tables of observed data. For tables of imputed data, such a subject's score for that period will be imputed by a modified last observation carried forward (mLOCF) rate-change method and rounded to the nearest whole number. Specifically, the substitution will be the subject's previous 7-day period score multiplied by the ratio of the mean within the same treatment regimen in the 7-day period of interest to the mean within the same treatment regimen in the previous 7-day period.

If a subject reports diary data for at least 4 days of a 7-day period, the scores for the period will be determined by the simple prorating method (discussed in Section [9.3.2.5](#)).

For example, for imputation of the 28-day period, the substitution will be iterative by 28-day period, in that imputation of a given 28-day period (e.g., Week 8) will follow

imputation of the preceding 28-day period (e.g., Week 4). The following is an example of how the mLOCF algorithm works:

Observed data:

Subject #	Treatment	Headache Day Count				
		Baseline	Week 4	Week 8	Week 12	Week 16
100001	TRT-A	14	12	13	---	---
100002	TRT-A	10	9	9	8	6
100003	TRT-A	12	13	10	8	5
100004	TRT-A	6	6	5	6	4
Mean	TRT-A	10.5	10	9.25	7.33	5

The Subject 100001 missing headache day count at Week 12 will be estimated by $13 * (7.33/9.25) = 10.3$, rounded to 10. So, the data set becomes:

Modified LOCF (mean-change adjusted LOCF) imputation:

Subject #	Treatment	Headache Day Count				
		Baseline	Week 4	Week 8	Week 12	Week 16
100001	TRT-A	14	12	13	10	---
100002	TRT-A	10	9	9	8	6
100003	TRT-A	12	13	10	8	5
100004	TRT-A	6	6	5	6	4
Mean	TRT-A	10.5	10	9.25	8	5

To estimate the headache day count of Week 16 for Subject 100001, this imputed value (10) will be used to update the overall mean for Week 12, which becomes $(10+8+8+6)/4 = 8$. Then the headache day count for Subject 100001 of Week 16 will be estimated by $10 * (5/8) = 6.25$, rounded to 6. So, the data set becomes:

Modified LOCF (mean-change adjusted LOCF) imputation:

Subject #	Treatment	Headache Day Count				
		Baseline	Week 4	Week 8	Week 12	Week 16
100001	TRT-A	14	12	13	10	6
100002	TRT-A	10	9	9	8	6
100003	TRT-A	12	13	10	8	5
100004	TRT-A	6	6	5	6	4
Mean	TRT-A	10.5	10	9.25	8	5.25

9.3.3 Main Analysis of Primary Efficacy Endpoint

The attributes of the estimand corresponding to the primary efficacy objective are summarized in [Table 1](#).

Table 1. Summary of the Estimand Attributes Corresponding to the Primary Efficacy Objective

Estimand Label	Attributes of the Estimand				
	Treatment	Endpoint	Population	Handling of Intercurrent Events	Statistical Summary
Primary	Arm A: Placebo Arm B: BOTOX 155 U Arm C: BOTOX 195 U	Change from baseline in the frequency of monthly migraine days across Months 5 and 6	The Intent-to-Treat (ITT) Population	IE1: Missing data due to study discontinuations will not be imputed and will be handled as MAR with MMRM. IE2: Regardless of whether rescue medications are taken or not, collected data will be included in the analysis. IE3: Subjects who discontinue study treatment due to any reason will have their data collected after discontinuation of study treatment, and collected data will be included in the analysis.	The difference in the change from baseline in the frequency of monthly migraine days across Months 5 and 6 between each BOTOX dose group and placebo

A mixed model for repeated measures (MMRM) analysis will be used for the primary analysis, using data for baseline and each month of the double-blind, placebo-controlled phase (i.e., months ending with Weeks 4, 8, 12, 16, 20, and 24). The statistical model will include treatment (BOTOX 195 U, BOTOX 155 U, and placebo), month, country, strata of [REDACTED], and treatment group-by-month interaction as fixed effects, with the baseline number of monthly migraine days as a covariate, included as a continuous variable rather than as the binomial stratification variable. Subject and residual errors will be random effects. Model parameters will be estimated using a restricted maximum likelihood method incorporating all observed data during the double-blind phase. Unstructured covariance structure will be used. Toeplitz or compound symmetry may be considered if convergency issues arise for the unstructured covariance structure. The Kenward-Roger approximation will be used to estimate denominator degrees of freedom. Contrasts will be constructed to obtain the average treatment effects across Months 5 and 6 to compare each BOTOX dose (195 U and 155 U) to placebo group. The ITT population will be used for primary and sensitivity analyses. A few subjects (less than 1%) who did not have post-baseline scores will not be included in the primary MMRM due to having missing values for the dependent variable. These subjects will be included in sensitivity analyses and have post-baseline scores imputed as described in Section 9.2. The primary comparisons of interest will be the pairwise comparisons of each BOTOX dose (195 U and 155 U) versus placebo across Months 5 and 6.

Each dose comparison will be analyzed across primary and secondary endpoints in the order described in Section 13.0, using a ranked-order serial gatekeeping approach to control the overall type I (false positive) error rate. For each BOTOX dose versus placebo, each variable/dose pair will be examined for significance only if significance was determined for all variable/dose pairs ranked ahead of it.

A 2-sided test with a p-value ≤ 0.05 will be considered as statistically significant for the treatment group comparisons of each BOTOX dose (BOTOX 195 U and BOTOX 155 U) versus placebo.

Interaction effects will be examined at the 0.10 level by including treatment group-by-country interaction in a separate expansion of the primary MMRM model. If there is a significant interaction ($p \leq 0.10$) in the expanded MMRM model, the relevant reduced model will be examined for interpretation (i.e., by country).

9.3.4 Sensitivity and Supplementary Analyses of the Primary Efficacy Endpoint

A sensitivity analysis will use the same MMRM model after imputation of missing data by the mLOCF rate-change method, which adjusts the most recent observation by the average change since that observation within the same treatment regimen. This method has been chosen for consistency with methods used for the Phase 3 CM studies of BOTOX.

An additional sensitivity analysis will use the same MMRM, after imputation of missing values by the mLOCF rate-change method, but with imputation instead by reversion toward baseline for post-baseline data (including missing and non-missing observed data) after the date of intercurrent events (e.g., took rescue medications, skipped Week 12 injection but staying in the study, exit due to lack of efficacy, due to adverse events or due to lost to follow-up) that could affect the primary endpoint.

In order to examine the sensitivity of the assumption, which relies on a missing at random/missing completely at random missing-data mechanism (MAR/MCAR), a sensitivity analysis will instead impute a subject's missing scores as the average non-missing score across all previous 28-day periods, including baseline, for the subject. This is defined as "reversion toward baseline" imputation. The reason for this adjustment is that such missing scores might be non-ignorable due to a missing not at random mechanism (MNAR) and the mLOCF assumption of continued effect could be misleading for such subjects, especially regarding the placebo component of any improvement from baseline. This sensitivity imputation will likely dampen down the mean improvement from baseline within treatment groups, but the interest will be in how it affects the treatment comparisons. If conclusions about treatment differences using observed data

and the sensitivity imputations are not qualitatively consistent, the reasons will be explored.

Another sensitivity analysis will use the same MMRM model after imputation of missing data by the multiple imputation (MI) method. The missing values of monthly migraine days will be imputed on the 0 to 28 scale by treatment group with 30 imputed datasets, using the fully conditional specification (FCS) method for ordinal data (via SAS® procedure MI with FCS logistic statement). Changes from Baseline will be calculated after imputation of the monthly migraine days.

Thus, the sensitivity analyses for comparison to the primary analysis using observed data are planned to include the following analyses of the primary variable.

1. MMRM after mLOCF imputation within treatments
2. Reversion toward baseline
3. MI for monthly migraine days

As a supplementary analysis of the primary endpoint, secondary analyses of covariance (ANCOVAs) of the primary efficacy variable (monthly migraine days) will be made for each month of the double-blind, placebo-controlled phase (i.e., months ending with Weeks 4, 8, 12, 16, 20, and 24), using the same model as for the primary MMRM analysis, but without repeat measures (i.e., omitting fixed effect of month and treatment group-by-month interaction).

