7.3 Handling Potential Intercurrent Events for the Primary and Key Secondary Endpoints

The estimand corresponding to the primary objective of this study is displayed in Section 3.1. Among intercurrent events, it includes study discontinuations, especially if due to lack of efficacy or due to AEs. Also included are any significant protocol deviations that could affect the primary endpoint, such as taking rescue medication or not receiving the Week 12 treatment. A sensitivity analysis will impute scores differently for such intercurrent events (e.g., reversion toward baseline).

The primary analysis assumes that missing data are missing completely at random or missing at random. A sensitivity analysis will use the same model as the primary analysis after imputation of missing data by the modified last observation carried forward (mLOCF) rate-change method, which adjusts the most recent observation by the average change since that observation within the same treatment regimen. An additional sensitivity analysis, which is aimed at intercurrent events, will instead impute missing data by reversion toward baseline for subjects who have intercurrent events that could affect the primary endpoint. These sensitivity analyses will be described in more detail in the SAP.

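### The mLOCF sensitivity analysis reports a standard error, interval and p-value with no allowance for the imputation, so it agrees with the primary result too easily

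*SAP*

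**What the plan says.** The primary analysis is an observed-data MMRM: "Model parameters will be estimated using a restricted maximum likelihood method incorporating all observed data during the double-blind phase" (SAP 9.3.3). Among the sensitivity analyses, SAP 9.3.4 lists this one first: "A sensitivity analysis will use the same MMRM model after imputation of missing data by the mLOCF rate-change method". Protocol 7.3 says the same: "A sensitivity analysis will use the same model as the primary analysis after imputation of missing data by the modified last observation carried forward".

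The imputation is defined in SAP 9.3.2.7. It applies to a month with too few reported days ("If a subject reports any diary data for less than 14 days of a 28-day period"). For such a month, "the substitution will be the subject's previous 28-day period score multiplied by the ratio of the mean within the same treatment regimen", taken in the month of interest over the month before, and the result is rounded. The rule runs forward month by month, and filled values feed later ratios. In the worked example, "this imputed value (10) will be used to update the overall mean for Week 12".

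Neither section provides repeated draws, a bootstrap or any other variance adjustment. The one caution about mLOCF in SAP 9.3.4 is that assuming a continuing effect may mislead. That concerns bias, not the standard error. The stated reason for using mLOCF is comparability with the Phase 3 chronic migraine studies.

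**The concern.** A filled month is a function of the subject's own earlier count and a ratio shared by everyone in that arm. Two things follow. First, the month adds no new information, yet the model counts it as a full observation. Second, the ratio is itself an estimate, so if it is too low by chance in one arm, all of that arm's missing months are pulled down together. The filled values are therefore correlated within arm, while the MMRM treats subjects as independent. A ratio below 1 also shrinks the spread of the filled values, since the SD of r × X is r × SD(X).

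At stake is what the analysis can show. SAP 9.3.4 asks whether conclusions from the sensitivity imputations are qualitatively in line with those from observed data. The significance standard in SAP 9.3.3 is "A 2-sided test with a p-value ≤ 0.05 will be considered as statistically significant for the treatment group comparisons". A check with a standard error that is too small reaches that standard more often than the primary analysis does, so its agreement is weaker support than it appears.

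**Working it through.** **1. The plan's own example** (SAP 9.3.2.7, starting at "The Subject 100001 missing headache day count at Week 12 will be estimated by").
- Week 12: 13 × (7.33/9.25) = 10.30, rounded to 10. Updated arm mean (10 + 8 + 8 + 6)/4 = 8.
- Week 16: 10 × (5/8) = 6.25, rounded to 6. Updated arm mean (6 + 6 + 5 + 4)/4 = 5.25.

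All figures reproduce. The example confirms a single fixed value per missing month, reused as data. It does not by itself prove the variance point: with four subjects, the simple standard error of the arm mean falls at Week 16 (0.577 to 0.479) but rises at Week 12 (0.667 to 0.816) after filling.

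**2. Inputs.** From the documents: 259 per arm, 1:1:1, two-sided 0.05 (SAP 2.4), six monthly counts, and the 9.3.2.7 rule. Not available: the SD (redacted) and the missing rate at Months 5 and 6 (only that fewer than 1% lack any post-baseline score). Assumed: SD of change about 3.2 days, baseline mean 9.5 within 6 to 14, correlated months, monotone dropout with Month 1 always observed, and 5% to 30% missing by Month 6.

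**3. Method.** One dose-placebo pair was simulated with no true difference. Data completed by mLOCF were analysed by ANCOVA on the Month 5-6 mean, which stands in for the MMRM contrast because completed data are balanced. The comparator was an observed-data MMRM with unstructured covariance. There were 5,000 to 6,000 runs per row (Monte Carlo error about 0.3 points on a 5% rate).

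| Missing by Month 6 | Reported SE | Actual SE | Ratio | 95% CI coverage | mLOCF type I | Observed-data MMRM type I |
|---|---|---|---|---|---|---|
| 5%, at random | 0.278 | 0.282 | 0.98 | 94.4% | 5.6% | 5.3% |
| 10%, at random | 0.277 | 0.293 | 0.95 | 93.7% | 6.3% | 5.4% |
| 15%, at random | 0.277 | 0.293 | 0.95 | 94.0% | 6.0% | 4.6% |
| 20%, at random | 0.277 | 0.298 | 0.93 | 93.1% | 6.9% | 4.8% |
| 30%, at random | 0.277 | 0.319 | 0.87 | 91.0% | 9.1% | 5.2% |
| 10%, outcome-dependent | 0.278 | 0.293 | 0.95 | 93.5% | 6.4% | 4.8% |
| 20%, outcome-dependent | 0.275 | 0.315 | 0.87 | 91.1% | 9.0% | 5.3% |

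With no missing data the SE is 0.278, which agrees with 3.17 × √(2/259) = 0.279. In the at-random rows mLOCF reports essentially that value whatever the dropout. The error rates fit the ratios through type I ≈ 2Φ(−1.96 × ratio): 0.93 gives 6.8% and 0.87 gives 8.8%.

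**4. Dependence on the course of the monthly means** (3,000 runs per level, dropout at random; missing 10%, 20%, 25%).
- Flat means: ratio 0.984, 0.972, 0.974; type I 5.2%, 5.4%, 4.9%.
- Means falling 3 days from Month 1 to Month 6: ratio 0.955, 0.879, 0.852; type I 5.7%, 8.1%, 8.9%.

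**5. Range over all data models tried, dropout at random.**
- 10% missing: ratio 0.93-1.00, type I 5.2-6.8%.
- 20% missing: ratio 0.88-0.97, type I 5.4-8.5%.
- 30% missing: ratio 0.83-0.96, type I 6.0-10.2%.

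With virtually no missing data the ratio is 0.99 and type I error 5.0%, so the imputation is the cause.

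**6. Agreement with the primary.** At 20% missing at random and no effect, mLOCF alone is significant in 2.5% of trials and the MMRM alone in 0.3%. With a true difference of about 0.85 days, mLOCF is significant in 85.1% of trials and the MMRM in 82.1%; mLOCF is also significant in 99.3% of the trials where the MMRM is. High agreement is expected because both use the same data. The one-sided pattern of disagreement is the evidence.

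**The case against.** The strongest case against the point concerns size and weight, and much of it stands.

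- **Size is not known.** At 5% missing, or with flat monthly means, the problem nearly disappears. The plan also works to limit missing months: subjects who stop study drug stay in follow-up (Protocol 5.6), their data are used (SAP Table 1), 14 reported days make a month usable, and next-day recall is allowed.
- **Weight is limited.** mLOCF is one of three sensitivity analyses and lies outside the gatekeeping. SAP 9.3.4 also plans multiple imputation with 30 datasets, which can carry imputation uncertainty, although no pooling rule is named. The reversion-toward-baseline analysis does not help with variance: it too fills single values, and its intercurrent-event form builds on mLOCF.

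A reader might infer more than the documents support:
- *That the analysis looks more precise as more data go missing.* This is not general. The reported SE rose (0.260 to 0.265), stayed flat (0.277) or fell (0.250 to 0.242, and 0.306 to 0.295) depending on the scenario. What holds is that the loss of information is not properly charged.
- *That the ratio comes from completers.* In the worked example the Week 8 mean of 9.25 includes the subject who is missing later, and later means include filled values.
- *That type I error is 8-9% at 20-25% missing.* That is one part of a range that depends on the course of the means and on why subjects drop out.
- *That the primary conclusion is in doubt, or that robustness cannot be shown.* The primary MMRM uses observed data and held 4.6-5.4% error in these runs.

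**Conclusion.** The point holds for the mLOCF analysis: its standard error, interval and p-value omit the uncertainty of the imputation. With dropout at random, the understatement of the standard error is slight at 5% missing, about 0-7% at 10%, 3-12% at 20% and 4-17% at 30%. Type I error at 10%, 20% and 30% is about 5-7%, 5-8.5% and 6-10%. Outcome-dependent dropout of 20% gave a 13% understatement and 9.0% error. The effect is smallest with flat monthly means and larger when they fall. All of this rests on an assumed SD, correlation, course of means and missing rate, and on ANCOVA in place of the MMRM contrast. The mLOCF point estimate was close to unbiased under random dropout, so the fault shown is in the variance. The primary result and the gatekeeping stand. The change is worth making because, as written, mLOCF is a check that tilts toward agreement.

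**What to change.** In SAP 9.3.4, choose one of two.

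1. Keep the mLOCF point estimate, and take its standard error, interval and p-value from a bootstrap. Resample subjects within arm, and within stratum and country where numbers allow. In each of at least 1,000 resamples, repeat the 9.3.2.7 imputation with re-estimated ratios and refit the model. In a simulation check the mean bootstrap SE was 0.267 at 10% missing and 0.279 at 20%, against actual values of 0.267 and 0.280 and a reported 0.259. Type I error at 20% was 4.7% (600 trials).
2. Present the mLOCF estimate descriptively, without a p-value, and state that the planned multiple imputation, pooled by Rubin's rules, carries the inference.

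Both keep comparability with the chronic migraine studies. The cost is SAP wording and, for the first option, computing time and a wider interval. From the ratios above, the widening is up to 1/0.93 = 1.08 times at 10% missing, 1/0.97 to 1/0.88 = 1.03 to 1.14 times at 20%, and 1/0.96 to 1/0.83 = 1.04 to 1.20 times at 30%.

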9.4 Secondary Efficacy Endpoints and Analyses

9.4.1 Secondary Efficacy Endpoints

The secondary endpoints are listed below:

1. Change from baseline in the frequency of monthly headache days across Months 5 and 6

2. Responder status of 50% reduction from baseline in the frequency of monthly migraine days across Months 5 and 6
3. Change from baseline in the frequency of monthly acute headache medication days across Months 5 and 6
4. Change from baseline in Migraine-Specific Quality of Life Questionnaire version 2.1 (MSQ v2.1) Role Function Restrictive (RFR) domain score at Month 6
5. Change from baseline in the Activity Impairment in Migraine Diary (AIM-D) Physical Impairment domain score across Months 5 and 6 (total 6-item Headache Impact Test [HIT-6] score for EU)

9.4.2 Main Analyses of Secondary Efficacy Endpoints

The attributes of the estimands corresponding to the secondary efficacy objectives are summarized in [Table 2](#).

Table 2. **Summary of the Estimand Attributes Corresponding to the Secondary Efficacy Objectives**

Attributes of the Estimand					
Estimand Label	Treatment	Endpoint	Population	Handling of Intercurrent Events	Statistical Summary
Secondary 1	Arm A: Placebo Arm B: BOTOX 155 U Arm C: BOTOX 195 U	Change from baseline in the frequency of monthly headache days across Months 5 and 6	ITT Population	IE1: Missing data due to study discontinuations, will not be imputed and will be handled as MAR with MMRM. IE2: Regardless of whether rescue medications are taken or not, collected data will be included in the analysis. IE3: Subjects who discontinue study treatment due to any reason will have their data collected after discontinuation of study treatment, and collected data will be included in the analysis.	The difference in the change from baseline in the frequency of monthly headache days across Months 5 and 6 between each BOTOX dose group and placebo

Attributes of the Estimand					
Estimand Label	Treatment	Endpoint	Population	Handling of Intercurrent Events	Statistical Summary
Secondary 2	Arm A: Placebo Arm B: BOTOX 155 U Arm C: BOTOX 195 U	Responder status of 50% reduction from baseline in the frequency of monthly migraine days across Months 5 and 6	ITT population	IE1: Missing data due to study discontinuations, will not be imputed and will be handled as MAR with MMRM. IE2: Regardless of whether rescue medications are taken or not, collected data will be included in the analysis. IE3: Subjects who discontinue study treatment due to any reason will have their data collected after discontinuation of study treatment, and collected data will be included in the analysis.	The odds ratio in participants responder status of 50% reduction from baseline in the frequency of monthly migraine days across Months 5 and 6 between each BOTOX dose group and placebo

Attributes of the Estimand					
Estimand Label	Treatment	Endpoint	Population	Handling of Intercurrent Events	Statistical Summary
Secondary 3	Arm A: Placebo Arm B: BOTOX 155 U Arm C: BOTOX 195 U	Change from baseline in the frequency of monthly acute headache medication days across Months 5 and 6	ITT Population	IE1: Missing data due to study discontinuations, will not be imputed and will be handled as MAR with MMRM. IE2: Regardless of whether rescue medications are taken or not, collected data will be included in the analysis. IE3: Subjects who discontinue study treatment due to any reason will have their data collected after discontinuation of study treatment, and collected data will be included in the analysis.	The difference in the change from baseline in the frequency of monthly acute headache medication days across Months 5 and 6 between each BOTOX dose group and placebo

Attributes of the Estimand					
Estimand Label	Treatment	Endpoint	Population	Handling of Intercurrent Events	Statistical Summary
Secondary 4	Arm A: Placebo Arm B: BOTOX 155 U Arm C: BOTOX 195 U	Change from baseline in Migraine- Specific Quality of Life Questionnaire version 2.1 (MSQ v2.1) Role Function – Restrictive (RFR) domain score at Month 6	ITT population	IE1: Missing data due to study discontinuations, will not be imputed and will be handled as MAR with MMRM. IE2: Regardless of whether rescue medications are taken or not, collected data will be included in the analysis. IE3: Subjects who discontinue study treatment due to any reason will have their data collected after discontinuation of study treatment, and collected data will be included in the analysis.	The difference in the change from baseline in Migraine- Specific Quality of Life Questionnaire version 2.1 (MSQ v2.1) Role Function – Restrictive (RFR) domain score at Month 6 between each BOTOX dose group and placebo

Attributes of the Estimand					
Estimand Label	Treatment	Endpoint	Population	Handling of Intercurrent Events	Statistical Summary
Secondary 5a	Arm A: Placebo Arm B: BOTOX 155 U Arm C: BOTOX 195 U	Change from baseline in the Activity Impairment in Migraine – Diary (AIM-D) Physical Impairment domain score across Months 5 and 6 in US	ITT Population	IE1: Missing data due to study discontinuations, will not be imputed and will be handled as MAR with MMRM. IE2: Regardless of whether rescue medications are taken or not, collected data will be included in the analysis. IE3: Subjects who discontinue study treatment due to any reason will have their data collected after discontinuation of study treatment, and collected data will be included in the analysis.	The difference in the change from baseline in the Activity Impairment in Migraine – Diary (AIM-D) Physical Impairment domain score across Months 5 and 6 between each BOTOX dose group and placebo

Attributes of the Estimand					
Estimand Label	Treatment	Endpoint	Population	Handling of Intercurrent Events	Statistical Summary
Secondary 5b	Arm A: Placebo Arm B: BOTOX 155 U Arm C: BOTOX 195 U	Change from baseline in the total 6-item Headache Impact Test [HIT-6] score across Months 5 and 6 in Europe	ITT population	IE1: Missing data due to study discontinuations, will not be imputed and will be handled as MAR with MMRM. IE2: Regardless of whether rescue medications are taken or not, collected data will be included in the analysis. IE3: Subjects who discontinue study treatment due to any reason will have their data collected after discontinuation of study treatment, and collected data will be included in the analysis.	The difference in the change from baseline in the total 6-item Headache Impact Test [HIT-6] score across Months 5 and 6 between each BOTOX dose group and placebo

Each dose comparison will be analyzed across primary and secondary endpoints in the order described in Section 13.0, using a ranked-order serial gatekeeping approach to control the overall type I (false-positive) error rate. For each BOTOX dose versus placebo, each variable/dose pair will be examined for significance only if significance was determined for all variable/dose pairs ranked ahead of it.

The comparisons of interest for each of these secondary endpoints will be the pairwise comparisons of each BOTOX dose (195 U and 155 U) versus placebo, with no statistical comparison between the BOTOX doses.

The analysis results of the change from baseline in monthly headache days, monthly acute headache medication days, AIM-D Physical Impairment domain score (or HIT-6 score

[for Europe]), and MSQ v2.1 RFR domain score at Month 6 will come from the same type of MMRM analysis of observed data used for the primary efficacy endpoint, except that the baseline covariates will be monthly headache days, monthly acute headache medication days, AIM-D Physical Impairment domain score (or HIT-6 score [for Europe]), and MSQ v2.1 RFR domain score, respectively.

Logistic regression will be used to analyze responder variables using the same ANCOVA analysis model described for the primary variable (i.e., the MMRM model used for the primary analysis, but without repeat measures). The proportion of subjects with at least 50% reduction in the change from baseline in monthly migraine days across Months 5 and 6 will be summarized, along with p-values from the logistic regression. The primary assessment will be the pairwise comparison of each BOTOX dose versus placebo.

